10.9. Appendix 9: CDC Classification for HIV infection (2014)

- Note that the CD4+ T-lymphocyte count takes precedence over the CD4+ T lymphocyte percentage in HIV infection stages 1, 2, and 3. The CD4+ T lymphocyte percentage should only be considered if the count is missing.
- **HIV infection, stage 0**
- Indicates early HIV infection, inferred from a negative or indeterminate HIV test result within 180 days of a positive result. The criteria for stage 0 supersede and are independent of criteria used for other stages.

- **HIV infection, stage 1**
- Laboratory confirmation of HIV infection with no AIDS-defining condition, and
 - CD4+ T-lymphocyte count of ≥ 500 cells/ μ L, or
 - CD4+ T-lymphocyte percentage of total lymphocytes of $\geq 26\%$.
- **HIV infection, stage 2**
- Laboratory confirmation of HIV infection with no AIDS-defining condition, and
 - CD4+ T-lymphocyte count of 200 to 499 cells/ μ L, or
 - CD4+ T-lymphocyte percentage of total lymphocytes of 14% to 25%.
- **HIV infection, stage 3 (AIDS)**
- Laboratory confirmation of HIV infection, and
 - CD4+ T-lymphocyte count of < 200 cells/ μ L, or
 - CD4+ T-lymphocyte percentage of total lymphocytes of $< 14\%$, or
 - Documentation of an AIDS-defining condition (see below).
- Documentation of an AIDS-defining condition supersedes a CD4+ T-lymphocyte count of > 200 cells/ μ L and a CD4+ T-lymphocyte percentage of total lymphocytes of $> 14\%$.
- **HIV infection, stage unknown**
- Laboratory confirmation of HIV infection, and
 - No information on CD4+ T-lymphocyte count or percentage, and
 - No information on presence of AIDS-defining conditions.
- **Stage-3-defining opportunistic illnesses in HIV infection**
- Candidiasis of bronchi, trachea, or lungs
- Candidiasis of oesophagus
- Cervical cancer, invasive
- Coccidioidomycosis, disseminated or extrapulmonary
- Cryptococcosis, extrapulmonary
- Cryptosporidiosis, chronic intestinal (> 1 month's duration)
- Cytomegalovirus disease (other than liver, spleen, or nodes), onset at age > 1 month
- Cytomegalovirus retinitis (with loss of vision)
- Encephalopathy, HIV-related
- Herpes simplex: chronic ulcers (> 1 month's duration) or bronchitis, pneumonitis, or oesophagitis (onset at age > 1 month)
- Histoplasmosis, disseminated or extrapulmonary
- Isosporiasis, chronic intestinal (> 1 month's duration)

- Kaposi's sarcoma
- Lymphoma, Burkitt's (or equivalent term)
- Lymphoma, immunoblastic (or equivalent term)
- Lymphoma, primary, of brain
- Mycobacterium avium complex or Mycobacterium kansasii, disseminated or extrapulmonary
- Mycobacterium tuberculosis of any site, pulmonary, disseminated or extrapulmonary
- Mycobacterium, other species or unidentified species, disseminated or extrapulmonary
- Pneumocystis jirovecii pneumonia
- Pneumonia, recurrent
- Progressive multifocal leukoencephalopathy
- Salmonella septicaemia, recurrent
- Toxoplasmosis of brain, onset at age >1 month
- Wasting syndrome attributed to HIV.

## VERSION HISTORY

SAP Version	Approval Date	Protocol Version (Date) on which SAP is Based	Change	Rationale
SAP	17 Oct 2023	Version 1 (01 June 2023)	Not Applicable	Original version
Amendment 1	30 Aug 2024	Amendment 1 (06 Oct 2023)	Section 1.2 study design updated to include Part 2 information  Added a footnote in section 4.7 to indicate interim analysis has taken place  Appendix 6.2 eCOA compliance added	To include Part 2 eCOA compliance requirement

## 1. INTRODUCTION

The purpose of this SAP is to describe the planned analyses to be included in the CSR for Study 212580. Details of the planned interim analysis, as well as the final analyses, are provided.

### 1.1. Objectives, Estimands and Endpoints

[figure not shown]
Objectives	Endpoints
Primary	

 
To evaluate the antiviral activity of VH3739937 in HIV-1 infected TN participants during 7 days of monotherapy
 
	
 
Maximum change from baseline (Day 1) in plasma HIV-1 RNA through Day 8
 

Secondary	

 
To assess the safety and tolerability of VH3739937 when administered as monotherapy over 7 days in HIV-1 infected TN participants
 
	
 
Incidence of SAEs, Deaths and AEs leading to Discontinuation through Day 8
 

 
To characterize the pharmacokinetics of VH3739937 in HIV-1 infected TN participants
 
	VH3739937 PK parameters : Following QD dosing: 
 
Day 1: Cmax, tmax, C24 and AUC(0-24)
 
Day 7: Cmax, tmax, C24, and AUC(0-24)
 
 Following single dose: Cmax, tmax, AUC(0-168) and C168
Exploratory	

 
To assess the safety and tolerability of VH3739937 when administered as monotherapy over time in HIV-1 infected TN participants
 
	
 
Incidence of AEs and severity of AEs through Day 25
 
Change from baseline and maximum toxicity grade increase from baseline for liver panel laboratory parameters (consisting of total and direct bilirubin, ALT, ALP and AST)
 

 
To assess the occurrence of Gag treatment emergent mutations or substitutions after 7 days of monotherapy with VH3739937
 
	
 
Genotypic assessment to detect any change in the Gag gene sequence from Day 1 to Day 8
 

 
To assess the immunologic effects of VH3739937 when administered over 7 days in HIV-1 infected adults
 
	
 
Change from baseline in CD4+ T-cell count through Day 8
 

 
To characterize the pharmacokinetics of VH3739937 in HIV-1 infected TN participants
 
	Additional VH3739937 PK parameters:

Objectives	Endpoints
	

• Following QD dosing (Day 7 only): CL/F, V/F and t1/2 will be determined if possible

• Following single dose: AUC(0-24) and C24, In addition, AUCinfinity, CL/F, V/F and t1/2 will be determined where possible

• To explore relationship(s) between plasma concentrations of VH3739937 and pharmacodynamic, efficacy and/or safety endpoints.

	

• Appropriate VH3739937 PK parameters with pharmacodynamic, efficacy and/or safety endpoints (e.g., change in plasma HIV-1 RNA, CD4+ cell count etc) may be explored as deemed appropriate

**CONFIDENTIAL**

[figure not shown]
212580

CCI

**CONFIDENTIAL**

CCI

## 1.2. Study Design

CCI

Design Features	

Phase IIa, PoC, multi-center, randomized, double-blind (sponsor unblinded), placebo-controlled adaptive study

Orally administered VH3739937 over 7 days in treatment naive HIV-1 infected adults

The study will evaluate the antiviral effect, safety, tolerability and PK/PD of VH3739937

Participants have a Screening visit approximately 7 to 14 days prior to first dose on Day 1

This study will be conducted in two parts:

Part 1: 20 TN HIV-1 infected adults will be randomized to one of 4 cohorts.

Part 2: 7 TN HIV-1 infected adults will be randomized to active treatment or placebo.

-----------------	--

Overview of Study Design and Key Features				
	
 
• Total duration of study participation is approximately 32 to 53 days based on the following: 
 
◦ 7 to 14 days, with a maximum of 28 days permitted for screening/qualification period
 
◦ 7 days for treatment with the study intervention and assessment at all planned visits
 
◦ 18 days for post-study intervention follow up visits including the final follow up visit. Participants will take cART throughout this period.
 
 
 
			
Study intervention	Part	Cohort Number	Number of Participants	Intervention
	1A	1	1	Placebo CCI [REDACTED]
		2	6	VH3739937 CCI [REDACTED] CCI [REDACTED]
		3	6	VH3739937 CCI [REDACTED] CCI [REDACTED]
	1B	1	1	Placebo CCI [REDACTED]
		4	6	VH3739937 CCI [REDACTED]
		2	1	Placebo CCI [REDACTED]
		5	6	VH3739937 CCI [REDACTED] CCI [REDACTED]
Study intervention Assignment	
 
• Part 1a: cohort 1 (placebo), cohort 2 or cohort 3 in a 1:6:6 ratio
 
• Part 1b: cohort 1 (placebo) or cohort 4 in a 1:6 ratio
 
• Part 2: cohort 1 (placebo) or cohort 5 in a 1:6: ratio.
 
			
Interim Analysis	
 
• An informal interim analysis will be conducted using available preliminary unvalidated in-stream unblinded clinical data once all participants (to include a minimum of 5 participants per active arm and 2 placebo participant) from Part 1 have, at a minimum, completed their Day 8 visit.
 
			

## 2. STATISTICAL HYPOTHESES

The primary objective of this study is outlined in Section 1.1 and will be addressed using an estimation approach (descriptive statistics) with no hypothesis testing. The primary treatment effect to be estimated is the maximum change from Baseline in plasma HIV-1 RNA over 7 days of VH3739937 treatment.

### 2.1. Multiplicity Adjustment

No adjustment for multiplicity will be made.

### 3. ANALYSIS SETS

Analysis Set	Definition	Analyses Evaluated
Screened	
 
• All participants who are screened for eligibility
 
	
 
• Study Population
 

Randomized	
 
• All participants who are randomly assigned to study treatment (i.e., VH3739937 or placebo) in the study
 
	
 
• Study Population
 

Safety	
 
• All randomized participants who take at least 1 partial or full dose of study treatment
 
• Participants will be analysed according to the treatment they actually received
 
	
 
• Safety
 

Full Analysis Set (FAS)	
 
• All randomized participants who received at least one full dose of study treatment
 
• Data will be reported according to the randomized study intervention
 
	
 
• Efficacy
 

Per-Protocol (PP)	
 
• All participants in the full analysis set for whom there were no major protocol deviations that impact the primary analyses
 
• Data will be reported according to the treatment actually received
 
• Specific details of major protocol deviations that would exclude participants from the PP analysis set are provided in Section 3.1
 
	
 
• Efficacy
 

Pharmacokinetic (PK)	
 
• All participants in the Safety analysis set who had at least 1 PK assessment (NQ values will be considered as non-missing values)
 
• Data will be reported according to the actual study treatment
 
	
 
• PK
 

### 3.1. Exclusions from the Per Protocol Analysis set

A participant meeting any of the following criteria prior to the end of part 1 will be excluded from the primary analysis based on the PP analysis set.

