**Table 1 Criteria leading to exclusion from Per Protocol Analysis set**

Number	Exclusion Description
01	Missed at least one dose
02	Took at least one incorrect dose
03	Missed the Day 1 or the Day 8 HIV-1 RNA assessment
04	Missed more than 1 post-Baseline HIV-1 RNA assessment between Day 1 and Day 7(inclusive)
05	Started the SoC medication prior to Day 8
06	Used strong or moderate CYP3A inducers (e.g., rifampin) or strong CYP3A/P-gp inhibitors (e.g., cobicistat, voriconazole) within 7 days (or 14 days if the drug is a strong CYP3A inducer) prior to Day 1 and through to Day 8*
07	Violated any of the inclusion or exclusion criteria.
08	
Met other Important Protocol Deviations occurring during the monotherapy period meriting exclusion from the PP analysis set as they have the potential to significantly impact primary analysis.
 
 
Protocol deviations will be adjudicated throughout the study conduct and will be classified as important (yes/no), along with determination on whether they should trigger exclusion from the PP analysis set and finalised prior to DBL
 

\*Medical monitor and PK lead will review the list of prior and concomitant medications used by participants in the study and determine which ones meet the criteria of strong/moderate inducers/inhibitors described here prior to DBL.

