### **4.2. Primary Endpoint(s) Analyses**

#### **4.2.1. Definition of endpoint(s)**

Plasma HIV-1 RNA values (copies/mL) will be used for the primary efficacy analysis. Change from baseline at the time point where the HIV-1 RNA is minimum (nadir) during the treatment period will be calculated for each participant in the original and log10 scales. The change from baseline at nadir is the primary endpoint used to construct the primary estimand (see Section 1.1.1). According to primary estimand definition (Section 1.1.1), if cART medication starts prior to Day 8 (for any reason), change from baseline values after cART initiation will be excluded from calculation of change from baseline at nadir.

Note, the change from baseline at nadir during monotherapy is typically the maximum change from baseline in HIV-1 RNA, or in other words the maximum Viral Load Decline (VLD). However, for participants who have all their post-baseline HIV-1 RNA values during treatment higher than the baseline value (e.g. as is the potential with some participants randomized to

placebo) the change from baseline at nadir is the minimum change from baseline. Also, if a (placebo) participant has a high increase from baseline in HIV-1 RNA and then a smaller decrease from baseline (or vice versa), the maximum change from baseline is at the point where HIV-1 RNA is its peak (zenith); the change from baseline at nadir will be used in this case in the primary analysis. From now on, in this document by “maximum change from baseline in HIV-1 RNA” during treatment we will mean the “change in HIV-1 RNA at nadir”.

The log10 transformation is used to allow for comparisons with data publicly available in the same scale from other compounds, and hence aid in interpretation.

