#### **4.2.2. Main analytical approach**

The primary efficacy analysis will be based on the Full Analysis Set.

Maximum change from baseline in plasma HIV-1 RNA during monotherapy will be summarized in original and log10 scale using descriptive statistics as described in Section [4.1.1](#).

Any missing HIV-1 RNA data (e.g., due to missed visits in the clinic, LFU or for any other reason) will not be imputed and will remain missing. Whatever HIV-1 RNA data are available for a participant during part-1 study and prior to starting cART will be used to calculate maximum VLD. Participants who withdraw from study prior to the end of the treatment period, preventing assessment of primary endpoint, no imputation will be performed for missed assessments after their study withdrawal.

All HIV-1 RNA data from all participants will be included in a listing.

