#### **4.2.3. Sensitivity analyses**

The primary analysis described in Section [4.2.2](#) will be repeated on the PP analysis set, and on the Safety analysis set if any participant receives treatment other than the one to which was randomized.

None of the IEs specified for the primary estimand are applicable for the PP analysis set, as none of them can occur in participants within the PP analysis set (because of criteria in [Table 1](#)). All available HIV-1 RNA data from the monotherapy period on the PP analysis set will be used for the sensitivity analysis.

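### SAP Amendment 1 adds Part 2, but the Per Protocol exclusions (3.1) and the primary-endpoint data rule (4.2.2) are still worded for Part 1 only

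*SAP*

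**What the plan says.** Section 1.2 of the SAP separates the two parts. Part 1 is 20 participants in Cohorts 1 to 4. For the second part it states "Part 2: 7 TN HIV-1 infected adults will be randomized to active treatment or placebo". The footnote to Section 4.7 confirms that the interim analysis has been done and that Part 2 will proceed.

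Section 3 sets the analysis sets with no limit by part. The Full Analysis Set (FAS) is "All randomized participants who received at least one full dose of study treatment". The Per Protocol (PP) set is the FAS without major deviations, and for the detail it adds "Specific details of major protocol deviations that would exclude participants from the PP analysis set are provided in Section 3.1".

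Section 3.1 then opens Table 1 with "A participant meeting any of the following criteria prior to the end of part 1 will be excluded from the primary analysis", continuing with a reference to the PP set. All eight criteria sit under that sentence.

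For the primary endpoint, Section 4.2.1 says that change from baseline at nadir "during the treatment period will be calculated for each participant in the original and log10 scales". Section 4.2.2 names the FAS and the monotherapy period, but its missing-data paragraph says "Whatever HIV-1 RNA data are available for a participant during part-1 study and prior to starting cART will be used to calculate maximum VLD".

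Section 4.2.3 says that the intercurrent events of the primary estimand do not apply to the PP set, "as none of them can occur in participants within the PP analysis set", and gives Table 1 as the reason.

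The version history for Amendment 1 lists changes to Section 1.2, the Section 4.7 footnote and Appendix 6.2. It lists none to 3.1 or 4.2.2.

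**The concern.** Both phrases use a label that the same SAP gives to Cohorts 1 to 4. Taken at their word, they leave Cohort 5 and its placebo participant with no PP exclusion criteria, and they drop those participants' HIV-1 RNA data from the calculation of maximum viral load decline. The second rule conflicts with the endpoint definition in the section just before it.

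Cohort 5 is the regimen added after an unblinded interim. The study is sponsor-unblinded, and Section 4.7 lists the statistician and the programmer among those with access to unblinded data. Whether a Part 2 participant leaves the PP set, and whether Part 2 data count, should not be settled by interpretation after results can be seen. The PP set also feeds more than one output: the sensitivity analysis in 4.2.3, the by-visit summaries in 4.2.4.1 and the mixed model in 4.2.4.2.

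**Working it through.** **1. The plan's own design figure.** Protocol Table 9 gives the full 95% CI width for the mean maximum decline at N = 6. The formula is width = 2 × t(0.975, 5) × SD / √6. For SD 0.40, 0.50, 0.65 and 0.80 it gives 0.840, 1.049, 1.364 and 1.679, against the stated 0.84, 1.05, 1.36 and 1.68. The table reproduces. It depends only on six participants per cohort, so the wording at issue does not change it.

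**2. Order of the parts.** Under Protocol 8.3.7 and 9.4, Part 2 is decided only after every Part 1 participant has completed Day 8, with enrollment paused for the review. A Part 2 participant's monotherapy therefore falls after all Part 1 monotherapy. The SAP gives no calendar definition of the end of Part 1. A calendar reading could at most catch someone dosed in Part 2 while Part 1 follow-up to Day 25 was still running, which would be an arbitrary rule.

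**3. Reach of each provision.**

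| Provision | Scope as written | Cohort 5 and its placebo participant |
|---|---|---|
| SAP 3, FAS | Randomized with one full dose, any part | Included |
| SAP 3, PP set | FAS without major deviations, any part; specifics left to 3.1 | Included, with no criteria of its own |
| SAP 3.1, lead-in to Table 1 | Criteria met before Part 1 ends | Not reached |
| SAP 4.2.1 | Each participant, treatment period | Included |
| SAP 4.2.2, opening | FAS, monotherapy | Included |
| SAP 4.2.2, missing data | Part 1 data before cART | Left out |
| SAP 4.2.3 | Relies on Table 1 to remove intercurrent events | Basis missing |
| SAP 4.7 | All primary endpoints, once all participants finish | Included |
| Protocol 9.3.2.2 | Study intervention, before cART | Included |

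The protocol offers no substitute list for the PP set: Section 9.3.1.1 leaves the deviations to the SAP. Section 3.1 with Table 1 is the only place where they are specified.

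The sentence in 4.2.2 closely follows the one in Protocol 9.3.2.2. The SAP has its Part 1 phrase where the protocol refers to study intervention.

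**4. How many participants.** From the intervention table in SAP 1.2:

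- Part 1: 1 + 6 + 6 + 1 + 6 = 20
- Part 2: 1 + 6 = 7
- Total: 20 + 7 = 27
- Active: 6 + 6 + 6 + 6 = 24; placebo: 1 + 1 + 1 = 3
- Outside the Part 1 wording: 7/27 = 25.9% of all, 6/24 = 25.0% of active, 1/3 = 33.3% of placebo

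All eight Table 1 criteria fall under the Part 1 lead-in.

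**The case against.** The strongest reply is that the intended rule can be recovered. Section 4.2.1, the FAS definition, the opening of 4.2.2, the end-of-study analysis in 4.7 and Protocol 9.3.2.2 all take in Cohort 5. Criterion 08 of Table 1 speaks of deviations "occurring during the monotherapy period meriting exclusion from the PP analysis set", and criteria 03 to 06 are tied to the participant's own study days. Section 6.1.3 requires review, before unblinding and database freeze, of all deviations that lead to exclusion, with no limit by part. On this view the Part 1 label is a leftover term for monotherapy.

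The practical stakes are also modest. The analysis is descriptive with no hypothesis test, results are shown by dose, and the PP set supports sensitivity and supplementary analyses only. The lead-in in 3.1 matters only if a Part 2 participant meets a criterion. The estimand text in 1.1.1 is redacted and may settle the scope.

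The points on intent and consequence stand, and so does the caution about 1.1.1. They do not remove the defect. Criteria 03 to 06 and 08 all sit under the sentence that limits them to Part 1. Section 6.1.3 sets a review process but supplies no criteria, and the general PP definition hands its detail back to 3.1. To reach the intended meaning, a reader must override a term that the SAP itself defines.

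A narrower objection concerns terminology: the schedule of activities and SAP 4.2.4.2 label the study intervention period as Days 1 to 7. The fix below writes out the day range, and SAP 6.1.1 treats that period as completed at the Day 8 visit, so it creates no real ambiguity.

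**Conclusion.** The concern holds. As written, 3.1 applies none of its eight exclusions to Part 2, and 4.2.2 leaves out Part 2 HIV-1 RNA data that 4.2.1 and the FAS include. The statement in 4.2.3 that Table 1 rules out intercurrent events therefore has no stated basis for Part 2. Seven of the 27 planned participants are affected: the whole of Cohort 5 and one of the three placebo participants. That share measures the reach of the wording and is not a predicted change in any result.

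The conclusion assumes that Part 1 in 3.1 and 4.2.2 means what Section 1.2 says it means, and that the planned numbers are randomized without replacements. The full list of intercurrent events in 1.1.1 could not be checked; early cART is visible in 4.2.1. This should be fixed before database lock.

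**What to change.** Make two phrase changes in the SAP and record both in the version history.

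- **Section 3.1:** replace the reference to the end of Part 1 with *up to and including the participant's scheduled Study Day 8, in Part 1 or Part 2*. Using the scheduled day keeps criterion 03 (missed Day 8 sample) and criterion 05 (cART before Day 8) workable when no pre-cART Day 8 sample exists. With no lower bound, criteria 06 and 07 still cover medication before Day 1 and eligibility violations.
- **Section 4.2.2:** replace the Part 1 phrase with *during the study intervention period (first dose through Day 8), in Part 1 and Part 2*, and keep the condition on starting cART. The On-Treatment Period Days 1-8 defined in SAP 6.3.1 would serve equally well as the period name.

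The cost is the two edits, made before database lock. No new data or analyses are needed.

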**Table 1 Criteria leading to exclusion from Per Protocol Analysis set**

Number	Exclusion Description
01	Missed at least one dose
02	Took at least one incorrect dose
03	Missed the Day 1 or the Day 8 HIV-1 RNA assessment
04	Missed more than 1 post-Baseline HIV-1 RNA assessment between Day 1 and Day 7(inclusive)
05	Started the SoC medication prior to Day 8
06	Used strong or moderate CYP3A inducers (e.g., rifampin) or strong CYP3A/P-gp inhibitors (e.g., cobicistat, voriconazole) within 7 days (or 14 days if the drug is a strong CYP3A inducer) prior to Day 1 and through to Day 8*
07	Violated any of the inclusion or exclusion criteria.
08	
Met other Important Protocol Deviations occurring during the monotherapy period meriting exclusion from the PP analysis set as they have the potential to significantly impact primary analysis.
 
 
Protocol deviations will be adjudicated throughout the study conduct and will be classified as important (yes/no), along with determination on whether they should trigger exclusion from the PP analysis set and finalised prior to DBL
 

\*Medical monitor and PK lead will review the list of prior and concomitant medications used by participants in the study and determine which ones meet the criteria of strong/moderate inducers/inhibitors described here prior to DBL.

